Title: Efficacy of the Autoimmune Protocol Diet for Inflammatory Bowel Disease

Date of Document: March 1, 2016 NCT number: (not yet assigned)

Study Protocol and Statistical Analysis Plan

Protocol ID: 16-6774

Sponsor: Scripps Health

Responsible Party: Principal Investigator, [name], MPH

Affiliation: Scripps Health

Study Start: September 1, 2016 (actual)

Primary Completion: December 10, 2016 (actual) Study Completion: December 10, 2016 (actual)

Title: Efficacy of the Autoimmune Protocol Diet for Inflammatory Bowel Disease PI: [name], MPH

1. SPECIFIC AIM: The aim of this study is to determine the potential efficacy of dietary therapy, the Autoimmune Protocol Diet (AIP Diet), in adult patients with active Crohn's disease (CD) or ulcerative colitis (UC).

2. RESEARCH DESIGN/METHODS:

- **A.** Primary Outcome Measure: Change in clinical disease activity for CD and UC from baseline to 11 weeks (study completion)
- For CD, clinical activity will be defined by the Harvey Bradshaw Index (HBI). Clinical remission is defined as a HBI<5, Clinical response is defined as a reduction in the HBI of at least 3 points.
- For UC, the Mayo Clinic Score (MCS) will be used to assess disease activity. Clinical remission is defined as a MCS of ≤2 and no subscore >1. Clinical response is defined as a reduction in the MCS of at least 3 points and a decrease of 30% from the baseline score, with a decrease of at least 1 point on the rectal bleeding subscale or an absolute rectal bleeding score of 0 or 1.
- **B.** Secondary Outcome Measures:
- For CD, changes in endoscopic activity will be defined by the Simple Endoscopic Score in Crohn's Disease (SES-CD) from most recent endoscopic evaluation prior to starting treatment with the AIP diet to 11 weeks (study completion). We will assess (a) Endoscopic remission, defined as an SES-CD of 0-2, and (b) Endoscopic response, defined as a decrease of 50% from the baseline SES-CD
- For patients with small intestinal CD not amenable to endoscopic evaluation, changes in inflammatory activity will be assessed by radiographic changes as measured by CT or MR enterography or video capsule endoscopy at baseline and 11 weeks (study completion).

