- For patients with UC, changes in endoscopic activity will be defined by the Mayo Clinic endoscopic subscore that comprises the MCS: We will assess (a) Endoscopic remission, defined as a Mayo endoscopic subscore of 0 or 1, and (b) Endoscopic response, defined as improvement in the Mayo endoscopic subscore by 1 point.
- Change in common laboratory measures, histologic activity, micronutrient levels (vitamin D, iron studies), use of steroids, and any adverse events resulting in flare or hospitalization from baseline to 11 weeks
- Where possible, assess changes in RNA expression from intestinal mucosal biopsy specimens from baseline to 11 weeks
- Assess changes in fecal microbial populations from baseline to 11 weeks, and compare with fecal microbial populations from IBD controls in clinical and endoscopic remission
- C. Study Design: Twenty participants with CD or UC with mild or moderate disease activity, as defined by HBI ≥ 5 for CD or Partial Mayo Clinic Score ≥ 3 for UC, ages 18 and over will enroll into this study for treatment with the AIP diet. Each patient will receive an initial evaluation including a physical exam, medication review, nutritional guidance and post treatment evaluations. We will also identify 10 patients with CD or UC in clinical and endoscopic remission and obtain a single stool sample for fecal calprotectin (inflammatory marker in stool) and microbiome analysis as our positive controls.
- Inclusion Criteria (Participants):
 - 1. At least 18 years of age

- 2. Able to provide written informed consent prior to screening and to comply with the requirements of the study protocol.
- 3. Established diagnosis of small bowel CD or colonic CD or ulcerative colitis
- 4. Confirmation of active CD or UC with recent (within 3 months) objective evidence of endoscopically active disease on colonoscopy or CT/MR enterography or video capsule endoscopy
- 5. Any medications being currently used for IBD must remain stable during the study period with the exception of tapering of corticosteroids.
- 6. Current disease activity defined as a Harvey Bradshaw index ≥ 5 at baseline for CD or Partial Mayo Score ≥ 3 for UC
- 7. Established Facebook account
- 8. Comfortable with internet-based surveys and email

- Exclusion Criteria (Participants):

- 1. If female, is pregnant or is breast feeding
- 2. Known celiac disease or subjects with a positive screen for celiac disease (elevated tissue transglutaminase antibodies)

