- Use of medications/supplements during study: Any medications, vitamins or supplements that participants are taking for at least 1 month prior to study initiation may be continued during the study period. During the 12 week study, however, participants will not be allowed to add, remove, or change doses any medications, vitamins or supplements, unless there are concerns related to IBD activity or flare, side effects or potential toxicity. The only exception to medication change is that steroid tapering will be allowed during the 12 week period. Any unanticipated changes to a patient's medication regimen will be recorded.
- Physician follow-up during study: Each participant will have clinical follow-up with their SCMG gastroenterologist during the week prior to enrollment, at 6 weeks, and at 11 weeks. Routine history and physical examination, as well as medication assessment, will be performed at these visits. In addition patients will undergo SOC blood work for CBC, HFP, vitamin D, iron studies, and CRP at 12 weeks. Fecal calprotectin will be performed at weeks 6 and 11.
- Intestinal biopsy and RNA sequencing: RNA-sequencing is a widely used next-generation sequencing technology which is used to study the expression patterns of genes in intestinal samples. A typical RNA-seq analysis pipeline involves demultiplexing of samples and quality control checks followed by alignment to a reference genome and finally counting the sequences aligned to various genes. The counts are then used to quantify expression levels of genes or compare samples using differential expression analysis. Where possible, patients undergoing endoscopic assessment at baseline will have 2 intestinal biopsy specimens collected in RNAlater for RNA sequencing. All patients will undergo standard of care endoscopic or radiographic reassessment of IBD activity at 11 weeks (study completion), with 2 intestinal biopsy specimens collected in RNAlater.

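### Clinical remission and response ignore steroid use, so remission on continuing, new or increased steroids counts for the diet, and a fall in steroid use cannot be separated from a taper already under way

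*Combined protocol and SAP*

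**What the plan says.** All references are to the combined protocol and SAP.

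- **Primary outcome (2.A).** For Crohn's disease, "Clinical remission is defined as a HBI<5". For ulcerative colitis, "Clinical remission is defined as a MCS of ≤2 and no subscore >1". Response is a fall in the same scores. None of these definitions mentions steroids.
- **Secondary outcomes (2.B).** The list of changes to be assessed includes "use of steroids, and any adverse events resulting in flare or hospitalization from baseline to 11 weeks". It does not say whether steroid use means dose, any use, or time off steroids. The endoscopic remission and response definitions also carry no steroid condition.
- **Medication rule, first statement (2.C, inclusion criterion 5).** IBD medications "must remain stable during the study period with the exception of tapering of corticosteroids".
- **Medication rule, second statement (2.C, use of medications/supplements during study).** Here the rule is that "participants will not be allowed to add, remove, or change doses any medications, vitamins or supplements, unless there are concerns related to IBD activity or" one of the other listed grounds, which are toxicity, side effects and a flare. The next sentence reads "The only exception to medication change is that steroid tapering will be allowed during the 12 week period". The paragraph ends: "Any unanticipated changes to a patient's medication regimen will be recorded".
- **Entry activity (2.C, inclusion criterion 6).** "Current disease activity defined as a Harvey Bradshaw index ≥ 5 at baseline for CD or Partial Mayo Score ≥ 3 for UC".
- **Analysis (2.D).** Paired t tests compare baseline with week 6 or week 11 in those with follow-up data, for each disease and for the whole cohort. Patients who continue, start, increase or taper steroids are not mentioned.

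**The concern.** The aim in section 1 is to determine the potential efficacy of the diet, so the before-after change will be read as its effect. Steroids are themselves a treatment for active disease and may change during the study. If the endpoint does not ask whether the patient was on them, two quite different results go into the same numerator: disease controlled without steroids, and disease controlled while steroids were continued, added or raised.

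The steroid-use outcome does not fill the gap, because it is listed separately and is not linked to remission. It also has an attribution problem of its own. Tapering may go ahead at any time with no stated link to response, so a dose that falls on a schedule fixed before entry would look like steroid sparing. What is at stake is whether the remission rate and the steroid result can be interpreted at all.

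**Working it through.** The plan gives no figure to reproduce: 20 participants are stated without power, effect size, standard deviation, expected rates, or the share on steroids. The check is therefore mainly a reading of the rules against the endpoints, with two short calculations.

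**Step 1. Routes by which a remission on steroids is counted.** Apply 2.A and 2.C together to a patient who scores HBI<5, or a Mayo score of 2 or less with no subscore above 1, at week 11.

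| Steroid status at week 11 | Allowed by the medication paragraph in 2.C? | Counted as remission under 2.A? |
|---|---|---|
| Off steroids | Yes | Yes |
| Continuing the entry dose | Yes, if taken for at least 1 month before initiation | Yes |
| Started or increased for disease activity or flare | Yes | Yes |

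The last column never changes, and 2.D does not separate the rows. The same holds for the score change in the paired t test: a fall in score that follows a steroid increase enters at full value.

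**Step 2. Whether a comparator could separate them.** It could not. Every participant with active disease receives the diet. The 10 controls are already in remission and give a single stool sample, so they say nothing about steroid use or remission without the diet.

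**Step 3. Effect on the remission rate.** Each patient whose status changes when steroids are taken into account moves the rate by 1/n. With n = 20, that is 1/20 = 5 points; 1 to 5 such patients give 5 to 25 points. Because 2.D analyses those with follow-up data and each disease separately, n may be smaller; with an assumed subgroup of 10, the step is 1/10 = 10 points. How many patients are affected cannot be derived from the documents.

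**Step 4. Direction of the steroid-use outcome with no diet effect.** Assume k baseline steroid users, each with probability q of tapering regardless of the diet and f of having the dose raised. The chance that more go down than up is

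P = Σ over d > u of [k! / (d! u! (k−d−u)!)] q^d f^u (1−q−f)^(k−d−u).

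With f = 0 this reduces to 1 − (1−q)^k: for k = 4, q = 0.3, 1 − 0.7^4 = 0.760; for k = 10, q = 0.5, 1 − 0.5^10 = 0.999. All values of k, q and f are assumptions.

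| q | f | k = 4 | k = 10 |
|---|---|---|---|
| 0.3 | 0 | 0.760 | 0.972 |
| 0.5 | 0 | 0.938 | 0.999 |
| 0.3 | 0.1 | 0.602 | 0.788 |
| 0.5 | 0.1 | 0.801 | 0.948 |
| 0.5 | 0.2 | 0.681 | 0.843 |
| 0.3 | 0.3 | 0.376 | 0.420 |
| 0.2 | 0.3 | 0.259 | 0.248 |

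A net reduction is close to certain only if increases never happen and tapering is common. Once increases for flare occur, the range is about 0.25 to 0.95. The rule tilts this outcome downward but does not fix its sign.

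**Step 5. Consistency of the medication rule.** Inclusion criterion 5 names steroid tapering as the sole exception to stability. The later paragraph adds flare, side effects and toxicity, and then calls tapering the only exception. The two statements contradict each other, and the second is inconsistent within itself.

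**The case against.** The best defence has four parts.

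- **The data are already collected.** Medications are documented at enrolment and assessed at weeks 6 and 11, unanticipated changes are recorded, and steroid use is a listed outcome. Anyone could cross-tabulate remission by steroid status. This stands, and it makes the fix cheap. It does not remove the gap: no such table is planned, and one chosen after the results are seen carries less weight.
- **Steroid use is not favourable by rule.** A reader might infer from the free taper that the steroid outcome can only improve. The documents do not support that. The medication paragraph allows changes for disease activity or flare, which is the obvious reason to start or raise steroids, and step 4 shows the direction is open.
- **There is no remission to maintain at entry.** A reader might speak of remission merely maintained by steroids. Inclusion criterion 6 requires active disease at baseline on current medication, so that description is inexact. The clearer cases are steroids added or increased during the study, and a late response to steroids already being taken. The entry rule protects only in part. The pre-study physician visit is in the week before enrolment, enrolment spans the 2 months before initiation, and a drug needs only 1 month of prior use. If the baseline score comes from that visit, steroids could be started after scoring and still be permitted.
- **The bias is not all in the diet's favour.** A reader might conclude that every effect here flatters the diet. Tapering can worsen HBI or Mayo scores and so work against the primary outcome. A patient who tapers fully with a stable score shows no change on the primary outcome, although the separate steroid outcome would record the improvement. This stands; distortion in either direction is a reason to report by steroid status.

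**Conclusion.** The concern holds as an omission in the endpoint definitions and the analysis plan. Followed as written, the plan credits the diet with remissions reached on continuing, new or increased steroids, and it cannot separate steroid sparing from a taper fixed before entry.

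The only size that follows from the documents is 5 percentage points per reclassified patient in a cohort of 20, and more if fewer are followed up. The total effect is unknown because the share on steroids and the frequency of starts, increases and tapers are not stated. The probabilities in step 4 are illustrations and not estimates. The documents do not support a claim that steroid use must fall, or that the overall bias must favour the diet.

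The point should be corrected because the remedy is small and uses planned data. It does not cure the single-arm design: a patient who finishes a pre-set course and improved because of it would still count as a steroid-free remission.

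**What to change.** Change the analysis and leave the medication rules as they are.

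1. In 2.A and 2.D, report week-11 remission and response by steroid status (off or on at week 11), and base the efficacy conclusion on steroid-free remission.
2. In 2.D, count patients who start or increase steroids during the study as non-responders in the efficacy analysis, with a sensitivity analysis that uses the score as observed.
3. In 2.B, keep the steroid-use outcome and define it as dose at baseline, week 6 and week 11. Add steroid-free remission among baseline steroid users. This should supplement the existing outcome and not replace it, since only the existing outcome captures steroid starts in patients who entered without them.
4. At enrolment, flag tapers prescribed before entry, and do not attribute those dose reductions alone to the diet.
5. Reconcile inclusion criterion 5 with the medication paragraph in 2.C, and that paragraph with itself, on which changes are allowed.

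The cost is a few sentences and one enrolment item, with no new visits or tests. The headline remission rate may be lower, and the baseline-user subgroup will be small and can only be descriptive.

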- 3. Inability to provide informed consent or unwilling to participate
- 4. Evidence of untreated infection (e.g. Clostridium difficile)
- 5. Presence of stoma or J pouch
- 6. Bowel surgery within 12 weeks prior to enrollment and/or has surgery planned or deemed likely for IBD during the study period
- 7. Use of oral or intravenous antibiotics within 4 weeks prior to study initiation
- 8. Use of tube or enteral feeding, elemental diet, or parenteral alimentation within 4 weeks prior to study initiation
- Study Process: (Note: SOC indicates standard of care)
 - Enrollment: Enrollment will take place over 2 months prior to study initiation. Participants will be screened by SCMG gastroenterologists, and informed consent will be obtained by the study coordinator (SC). At enrollment, the SC will document relevant history and physical examination, current prescription and nonprescription medications, and any imaging, endoscopic, and histologic evaluation completed for IBD. Participants will undergo SOC stool testing for common infections (unless completed within 3 months) and one 5mL blood draw into PAX tube for future genotyping.
 - 1 week prior to study initiation: Participants will undergo SOC testing for CBC, HFP, vitamin D, iron studies, CRP, and fecal calprotectin. They will also establish online membership in the "SAD (Standard American Diet)-to-AIP (Autoimmune Paleo) Diet Transition Program" run by [name], and receive two books on AIP diet and recipes ("The Paleo Approach: Reverse Autoimmune Disease and Heal Your Body" by Ballantyne and "The Autoimmune Paleo Cookbook: An Allergen-Free Approach to Managing Chronic Illness" by Trescott).
 - Study initiation/Treatment with AIP diet: Intervention will be based on a 6-week transition to the AIP diet and 6-week maintenance phase on the AIP diet (no food group reintroduction allowed), using the "SAD-to-AIP Diet Transition Program." Patients will receive certified health coaching and one-on-one and group guidance by a registered dietician, along with group-based coaching through a private and secret Facebook group. During the study, participants will record daily dietary intake, which

will be reviewed by program team. They will also complete surveys regarding feasibility, tolerability, and adherence to AIP diet every 3 weeks during the study.

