- Microbiome Analysis: 16S ribosomal RNA sequencing is a commonly used method to identify and quantify microbial species in a microbiome sample. Sequencing can be performed using an Illumina MiSeq machine which outputs anywhere from 10-20 Million paired-end 300 bp reads. Analysis will be performed using "mothur," an open-source software, with subsequent pipeline steps obtained to estimate species diversity and subtypes. Stool assessment for microbiome analysis from participants will be performed during the week prior to study initiation, and weeks 2, 4, 6, and 11. Stool assessment from positive controls will be performed during enrollment or the study period.

D. Statistical Analysis:

Analyses for the primary outcome will be conducted for participants with CD or UC and for the entire cohort. Paired t test will be used to examine differences between baseline and week 6 or 11 outcomes among those with follow-up data at those time points. Fisher's exact test will be used to examine whether IBD type is associated with the primary outcome. Survey data will be analyzed using descriptive statistics, including frequencies, percentages, means, and modes, as well as ANOVA. Relationships between bivariate categorical variables, including diet adherence and IBD type, will be tested using Chi-Square or Fisher's Exact Test, as appropriate.

RNA analyses: To identify genes which are differentially expressed due to the dietary intervention, we will first control for patient level differences using a Bayesian hierarchical mixture model, which estimates the log fold change for each gene and calculates a probability of the gene being differentially expressed (P(DE)). Significant genes will be selected considering a 5% Type 1 error rate i.e. P(DE)>0.95. Gene Ontology enrichment will be done for significantly up-regulated and down-regulated gene using DAVID. DAVID is a web-based application that ranks biologically relevant gene sets enriched in the gene list being interrogated using a modified Fisher Exact test.

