Microbiome analyses: 16S ribosomal RNA sequencing is a commonly used method to identify and quantify microbial species in a microbiome sample. Sequencing will be performed using an Illumina MiSeq machine which outputs anywhere from 10-20 Million paired-end 300 bp reads. Analysis will be performed using "mothur," an open-source software, with subsequent pipeline steps obtained to estimate species diversity and subtypes. Stool assessment for microbiome analysis from participants will be performed using mail-in FTA cards during the week prior to study initiation, and weeks 2, 4, 6, and 11.

We will also identify at least 10 patients with CD or UC in clinical, endoscopic, and histologic remission and obtain a single stool sample using mail-in FTA cards for microbiome analysis as our positive controls. Stool assessment from positive controls will be performed during study enrollment or the study period to avoid any temporal bias. In this way we will be able to characterize whether, within 11 weeks of the AIP diet, the microbiome profile changes over time due to dietary intervention are on a trajectory towards normalization based on changes in the degree of similarity with profiles from IBD patients already in remission. Diversity within individual samples and similarity between individuals and time-points will be measured using diversity metrics commonly used in ecological studies. These summary metrics will be utilized to determine whether clinical response can be correlated to microbiome normalization or other diversity changes.

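### RNA and microbiome changes are credited to the diet in a single-arm before-after comparison, while drug changes permitted between samples enter neither analysis

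*Combined protocol and SAP*

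**What the plan says.** - **RNA (section 2.D, RNA analyses).** The stated aim and adjustment are: "To identify genes which are differentially expressed due to the dietary intervention, we will first control for patient level differences", which is to be done "using a Bayesian hierarchical mixture model, which estimates the log fold change for each gene". The selection rule is "Significant genes will be selected considering a 5% Type 1 error rate i.e. P(DE)>0.95". No medication term, exclusion or sensitivity analysis is named.
- **Microbiome (section 2.D, Microbiome analyses).** The question is whether "the microbiome profile changes over time due to dietary intervention are on a trajectory towards normalization", judged by similarity to single stool samples from IBD patients in remission. The diversity and similarity metrics are then to be related to clinical response. No adjustment of any kind is named.
- **Drug changes (section 2.C, use of medications and supplements).** Adding, removing or changing the dose of a drug is barred "unless there are concerns related to IBD activity or flare, side effects or potential toxicity". The next sentence reads: "The only exception to medication change is that steroid tapering will be allowed during the 12 week period". Unanticipated changes are to be recorded.
- **Inclusion criterion 5.** "Any medications being currently used for IBD must remain stable during the study period with the exception of tapering of corticosteroids".
- **Antibiotics.** They appear only in exclusion criterion 7: "Use of oral or intravenous antibiotics within 4 weeks prior to study initiation".
- **Sampling.** Biopsies for RNA are taken at baseline where possible and at week 11. Participants give stool in the week before initiation and at weeks 2, 4, 6 and 11; the remission controls give one sample each.

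**The concern.** Both analyses compare a patient with himself or herself at an earlier time, and every participant receives the diet. The remission controls show what stool looks like in remission, not how it would have changed over the same weeks without the diet. The before-after contrast therefore carries the whole weight of the word 'due', and anything else that changed between the samples is part of it.

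The plan itself foresees one such change, steroid tapering, and allows others. A steroid or other IBD drug changed between two biopsies may plausibly alter mucosal gene expression, and an antibiotic may plausibly alter stool flora. If so, drug-related shifts would be reported as the diet's mechanism, and nothing in section 2.D would show it. For the microbiome there is a second route. Tapers and flare treatment are likely to follow the clinical course, so a drug-related shift can also create or distort the planned correlation between microbiome metrics and clinical response.

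**Working it through.** The plan gives no sample size, power or frequency figure on this point, so there is nothing to reproduce. The check is mainly on the structure of the contrast, followed by an illustration under assumed values.

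**1. What patient-level control removes.** Write the measurement for patient i at time t as a_i + (diet effect δ if t is after baseline) + (drug effect γ if the drug regimen changed by t) + error. The paired change is

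D_i = δ + γ·M_i + error, where M_i = 1 if a drug changed between the samples.

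The term a_i cancels, and this is what controlling for patient differences achieves. The term γ·M_i does not cancel, because it arises within the patient. The mean change estimates δ + pγ, with p the share of patients who had a drug change, so the bias as a diet effect is pγ. The rule P(DE) > 0.95 does not help: it concerns whether expression changed, not why.

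**2. Size, for illustration only.** Inputs: 20 participants (section 2.C). Assumed, because the documents do not give them: p from 10% to 50%, and γ from 0.5 to 1.0 SD of the within-patient change. The rejection rates come from 40,000 simulated trials per setting, with no diet effect (δ = 0) and a two-sided 5% one-sample t test on the paired changes. This test stands in for a paired contrast; it is not the plan's Bayesian model.

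| Pairs | With a drug change | γ = 0.5 SD: bias; rejection | γ = 1.0 SD: bias; rejection |
|---|---|---|---|
| 20 | 2 (10%) | 2/20 × 0.5 = 0.05; 5.2% | 2/20 × 1.0 = 0.10; 5.9% |
| 20 | 5 (25%) | 5/20 × 0.5 = 0.125; 7.6% | 5/20 × 1.0 = 0.25; 14.3% |
| 20 | 10 (50%) | 10/20 × 0.5 = 0.25; 17.3% | 10/20 × 1.0 = 0.50; 46.9% |
| 10 | 5 (50%) | 5/10 × 0.5 = 0.25; 9.8% | 5/10 × 1.0 = 0.50; 21.7% |

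The last row matters for RNA. Baseline biopsies are taken only where possible, and some small-bowel Crohn's disease is followed by imaging or capsule (section 2.B), so there may be fewer than 20 pairs. With fewer pairs the same bias is less often declared significant, but it is no smaller.

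**3. How many stool samples one antibiotic course could touch.** Borrow the 4-week interval of exclusion criterion 7 and count the samples at weeks 2, 4, 6 and 11 that fall after a course ends:

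- ending between weeks 0 and 2: weeks 2 and 4, so 2 of 4;
- ending between weeks 2 and 4: weeks 4 and 6, so 2 of 4;
- ending between weeks 4 and 6: week 6, so 1 of 4;
- ending between weeks 6 and 7: none;
- ending between weeks 7 and 11: week 11, so 1 of 4.

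A sample taken while the course is running adds to these counts. A course in progress at week 2 that ends soon afterwards takes weeks 2, 4 and 6, so 3 of 4. A course that ends before week 7 leaves the baseline-to-week-11 comparison untouched.

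**4. The medication rules side by side.** Inclusion criterion 5 excepts only corticosteroid tapering, for IBD drugs. The medication paragraph first excepts changes for disease activity, side effects or toxicity, and then calls tapering the only exception. Which changes can occur between samples depends on how these are read together.

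**The case against.** The strongest reply is that these are secondary outcomes in a 20-patient study of potential efficacy, with RNA collected only where possible, and that the usual cure may do harm. Tapering and flare treatment happen after baseline and may result from how the patient fares on the diet. Entering steroid change in the RNA model, or making patients without drug changes the main contrast, conditions on a post-baseline variable. It can remove real diet effect and select patients who did not flare, and with at most 20 patients the adjustment would be weak. All of this stands. It is why the full-set contrast should remain the main one. It does not rescue the causal wording, because a change that came through a taper still cannot be told apart from one that came from the diet.

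It also stands that the plan is not blind to drug changes: unanticipated ones are recorded, medication is assessed at the physician visits, and steroid use is a secondary outcome. None of this reaches the RNA or microbiome analysis.

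A reader might infer more than the text supports:

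- *That antibiotics are an approved flare treatment.* They are never named as such. The exception in the medication paragraph names no drug class and no on-study rule mentions antibiotics, so the plan is silent.
- *That exclusion criterion 7 admits that antibiotics spoil samples.* It is an eligibility rule without a stated reason and does not mention stool.
- *That RNA results are to be correlated with clinical response.* That correlation is planned for the microbiome metrics only.

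**Conclusion.** The point holds. As written, section 2.D can report drug-related changes in expression or flora as effects of the diet. The RNA analysis adjusts only for patient-level differences and the microbiome analysis for nothing named, while drug changes between samples are permitted and unused.

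The size cannot be fixed from the documents, because neither the number of patients with a drug change nor the drug effect is given. Under the assumed ranges and 20 pairs, the distortion is negligible if about 10% of patients change a drug (rejection at most 5.9% against a nominal 5%) and serious if half do (up to 46.9%). The table takes the drug effect as positive; in practice its direction is unknown, and it could also mask a diet effect.

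It would be wrong to conclude that the trial's main result is undermined by this point. The primary clinical outcome does not depend on these analyses. What is at stake is what the trial can say about mechanism.

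**What to change.** In section 2.D, and where noted in 2.C:

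1. In both the RNA and the microbiome paragraphs, replace the causal phrase with 'during the dietary program'. This is needed even if few drugs change, because there is no concurrent group without the diet.
2. Keep the contrast in all available pairs and samples as the main analysis. Prespecify a sensitivity analysis that leaves out (a) RNA pairs with a steroid or other IBD drug change between the biopsies, and (b) stool samples taken during or within 4 weeks after an antibiotic, or after another recorded drug change. Repeat the correlation with clinical response on the remaining stool samples, and report how many pairs and samples were left out and why. The 4 weeks are borrowed from exclusion criterion 7 for convenience, and the text should say so.
3. Make sure that the dates of steroid tapers and antibiotic courses are captured. The medication paragraph commits only to recording unanticipated changes, and a permitted taper may not count as one.
4. Reconcile inclusion criterion 5 with the wider exception in the medication paragraph.

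The cost is some SAP wording, one subset analysis and the capture or retrieval of dates. The downside is fewer pairs and samples in the sensitivity analysis, which also selects on post-baseline events. It is therefore supportive only: agreement with the main contrast is reassuring, and disagreement is a warning, not a corrected estimate of the diet effect. The title block gives an actual completion date, so if the analyses have already been run, the sensitivity analysis should be labelled post hoc.
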